Spirometry measures will be collected, including full vital capacity and tidal volume using a handheld spirometer.

The nasal cannula flexible prongs will then be positioned within the participant's nares, curving downwards, with the tubing of the nasal cannula wrapped around and behind the ears. The tautness of the cannula will be adjusted to fit the participant comfortably.

The nasal cannula will be connected to the KayPENTAX Digital Swallow Workstation Swallowing Signals Lab equipment, which is located on a properly insulated cart with an uninterrupted power supply and isolation transformer. This equipment and procedure has been used in prior experiments in the PI's lab, with no history of adverse events.

Participants will be asked to swallow the barium stimuli previously developed in videofluoroscopy, with concurrent measurement of nasal airflow. Videofluoroscopy will be performed at maximum temporal resolution (30 pulses/second) and captured at 30 frames/second. Participants will be asked to swallow 3 boluses per stimuli type for a total of 18 bolus sips: 3 sips of thin barium; 3 sips per barium consistency prepared with a gum-based thickener (slightly, mildly, moderately, and extremely thick), and 3 sips of moderately thick barium prepared with a starch-based thickener. The stimuli will be presented in order of increasing consistency. Participants will be asked to take naturally sized sips of each stimulus from cups containing 40 ml. Cup weights will be measured before and after each sip on a digital balance so that sip volume and mass can be calculated.

Data Processing

The videofluoroscopy recordings will be spliced into single bolus clips and the audio channel will be muted to remove cues that might bias rating. Blinded videofluoroscopy rating will then be performed in duplicate by trained raters in the [name] Lab following established procedures. Discrepancies between raters will be flagged and resolved at consensus meetings, as required. These procedures will yield a large number of parameters for each swallow, as listed below:

- a) Bolus transit time from ramus of mandible to vallecular pit (in ms);
- b) Bolus dwell time in pharynx from ramus of mandible to laryngeal vestibule closure (in ms);
- c) Pharyngeal bolus transit time from ramus of mandible to upper esophageal sphincter opening (in ms);
- d) Bolus transit time from ramus of mandible to tail exiting the upper esophageal sphincter (in ms);

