- e) Laryngeal vestibule reaction time, from the onset of laryngeal elevation till full closure of the laryngeal vestibule is achieved (in ms);
- f) Amount of residual left behind in the valleculae and pyriform sinuses after the initial swallow (measured using the Normalized Residue Ratio Scale);

- g) Number of swallows for the bolus;

The airflow measurements collected via the nasal cannula will be rated in duplicate by trained raters in the [name] Lab. Discrepancies in ratings will be flagged and resolved at consensus meetings, as needed. The following airflow measurements will be collected and analyzed.

- a) Respiratory phase pattern pre- and post-swallow;
- b) Respiratory pause duration.

The following airflow measurements will be collected via the handheld spirometer. These measures will be recorded from the device by a research team member.

- a) Full vital capacity
- b) Tidal volume

Tracheal sounds and accelerometry will be collected using the Patch, providing data regarding flow rate and intensity.

Data Analysis

We will determine the extent to which parameters measured during ASPEKT rating (Analysis of Swallowing Physiology: Events, Kinematics, & Timing) differ between participants with spinal disorders and reference data from the [name] lab for healthy individuals (REB#15-9431-D). Data analyses will focus on evaluating whether the physiological parameters identified using ASPEKT, primarily laryngeal vestibule reaction time, explain differences in primary swallowing outcomes (Penetration-Aspiration score and pharyngeal residue) between groups. The primary respiratory outcome measures (respiratory phase pattern and pause duration) will be compared between participants with spinal disorders and data referenced from related studies evaluating these patterns in healthy adults (REB#15-9431-D). Using path analysis, the relationship between swallowing physiology and respiratory capacity may be illustrated, and the resulting effect on swallowing safety and efficiency in this population.

In addition, the relationship between stimulus consistency and the two primary outcomes (Penetration-Aspiration score and pharyngeal residue) will be analyzed to further our understanding of the impact of different liquid flow levels on swallowing function and physiology in the spinal disorders population.

Risks and Benefits

Risks

The following risks will be disclosed to all participants prior to obtaining their consent to participate:

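### Residue is read only after the initial swallow, with no pre-swallow reading or clearance rule, so 17 of 18 readings may include carry-over that runs in the same direction as consistency

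*Combined protocol and SAP*

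**What the plan says.** The Data Processing section lists residue once, at item f: "Amount of residual left behind in the valleculae and pyriform sinuses after the initial swallow", measured on the Normalized Residue Ratio Scale. No residue reading before the swallow is listed. Item g counts the swallows taken for each bolus but is not linked to the residue measure.

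Under Data Collection Procedures, "Participants will be asked to swallow 3 boluses per stimuli type for a total of 18 bolus sips", and "The stimuli will be presented in order of increasing consistency". No step to clear or check residue between boluses is described. The only clearing action in the protocol is the coughing and throat clearing encouraged when aspiration is seen (Risks, item d), and that is triggered by aspiration, not by residue.

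Rating is by bolus: "The videofluoroscopy recordings will be spliced into single bolus clips", and "Blinded videofluoroscopy rating will then be performed in duplicate by trained raters" under the laboratory's established procedures, which the protocol does not reproduce.

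Data Analysis uses residue twice. The physiological parameters are to "explain differences in primary swallowing outcomes (Penetration-Aspiration score and pharyngeal residue) between groups", and "the relationship between stimulus consistency and the two primary outcomes (Penetration-Aspiration score and pharyngeal residue) will be analyzed".

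**The concern.** A post-swallow reading records all the barium standing in the valleculae and pyriform sinuses at that moment, whichever bolus left it there. The plan assigns that amount to the bolus on the clip, and so to that bolus's consistency. Without a reading taken before the bolus arrives, the listed parameters do not show how much was already present.

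The consistency analysis is where this matters most. The thickest stimulus always comes last and the thin one always first, so a build-up of old barium over the session would look like an effect of thickness. The study is meant to inform the use of thickened liquids, so a spurious rise in residue with consistency is an error worth guarding against.

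**Working it through.** **Inputs from the protocol**

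- Stimuli and boluses (Data Collection Procedures): thin, four gum-thickened consistencies and one starch-thickened moderately thick stimulus, 3 boluses each.
- Order: fixed, thin to thick.
- Residue reading: after the initial swallow of each bolus (Data Processing, item f).

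**Step 1. Reproduce the plan's figure.** 3 + (3 × 4) + 3 = 18 boluses, as stated. In a complete sequence only the first has no barium before it, so 17 of 18 (94%) could carry residue forward.

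**Step 2. Illustrate the build-up.** The documents give no clearance figures, so what follows rests on assumption. Let every bolus leave the same own residue of 1 unit, so that there is no true consistency effect. Let a share c of each reading still be present at the next reading. Treat the amounts as additive. Then

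R(1) = 1, and R(k) = 1 + c × R(k−1), which gives R(k) = (1 − c^k) / (1 − c).

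First stimulus (boluses 1 to 3):

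- c = 0.25: (1 + 1.25 + 1.3125) / 3 = 1.19
- c = 0.50: (1 + 1.5 + 1.75) / 3 = 1.42

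Last stimulus (boluses 16 to 18), where R(k) has settled close to 1 / (1 − c):

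- c = 0.25: 1 / 0.75 = 1.33
- c = 0.50: 1 / 0.50 = 2.00

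| Assumed c | Mean reading, first stimulus | Mean reading, last stimulus | Last above first | Carry-over as share of all measured residue |
|---|---|---|---|---|
| 0 | 1.00 | 1.00 | 0% | 0% |
| 0.25 | 1.19 | 1.33 | 12% | 24% |
| 0.50 | 1.42 | 2.00 | 41% | 47% |

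The final column is 1 − 18 / ΣR(k). For c = 0.50, ΣR(k) = 34 and 1 − 18/34 = 47%.

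**Step 3. Read the pattern.** By stimulus, the means at c = 0.50 are 1.42, 1.93, 1.99, 2.00, 2.00 and 2.00. At c = 0.25 they are 1.19 and then 1.33 for each of the other five. Most of the artefact therefore falls between the thin stimulus and the rest. With full clearance (c = 0) there is none.

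**The case against.** The strongest reply is that nothing in the documents shows that residue persists. Item g expects further swallows after the initial one, which may clear it. Weighing the cup before and after each sip implies a pause. People with a prior history of swallowing difficulties are excluded, which may keep standing residue low. All of this stands, and it is why the point is that readings may include carry-over. A reader might go further and infer that the measure is not the residue the bolus produced. The text does not support that: the first bolus is exempt, and the others are affected only where old barium survives to the next reading.

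It is also fair to say that the parameter list is not complete. It leaves out the Penetration-Aspiration score, itself a primary outcome, so the absence of a pre-swallow reading does not prove that none is made. The rating procedures may already contain a rule. If so, stating it in the protocol settles that part.

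A reader might infer that carry-over inflates the spinal-versus-healthy difference. That needs unequal persistence in the two groups. If the true ratio is G, the settled ratio is G × (1 − c_healthy) / (1 − c_spinal), which equals G when the two shares are equal. The documents give neither share and do not say that the reference data used the same bolus sequence. Standing residue from poor clearance is also part of the inefficiency that the group comparison is meant to capture.

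Extending the point to Penetration-Aspiration scores is tempting too, but old residue entering the airway is still a safety event.

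Lastly, one may say that the real issue is the fixed order. The order gives carry-over its direction. A balanced order would spread it across stimuli but would not remove it from the second and third boluses of the same stimulus.

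**Conclusion.** The gap is real but limited. The plan does not say how barium present before a bolus is measured, cleared or allowed for, and residue is a primary outcome analysed by consistency. For 17 of 18 boluses the reading may include carry-over, and under the fixed order any carry-over is confounded with thickness.

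Its size is unknown. Under assumed shares of 0, 0.25 and 0.5, the last stimulus would read 0%, 12% and 41% above the first with no true difference. These figures rest on equal own residue for every bolus, a constant share carried forward and additive amounts. They illustrate the mechanism and are not estimates for this population.

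Reading residue after the initial swallow is not itself a fault; what is missing is the companion reading before it. The documents support a cheap improvement to the within-spinal consistency analysis. They do not support calling the endpoint invalid or the group comparison biased.

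**What to change.** 1. In item f, also rate residue, on the same scale, on the last frame before each bolus enters the pharynx. Where that frame was not recorded, use the last available residue reading of the previous clip and label it an approximation. If that reading precedes further swallows, it may overstate what was left.
2. In the within-spinal consistency analysis, adjust post-swallow residue for the pre-swallow value, or analyse the change. Adjustment assumes less: a simple change treats none of the standing barium as cleared by the new swallow.
3. In the comparison with healthy adults, keep the unadjusted post-swallow residue as the outcome. Pre-swallow residue is partly a result of impaired clearance, so adjusting for it could remove real group difference. Report it beside the outcome, and state whether the reference data were read the same way.
4. Do not exclude clips that start with residue, since that would tend to drop the most impaired participants.
5. If the rating procedures already have a rule for residue present before a bolus, state it.

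The cost is one more frame to trace per clip by the existing raters, on recordings already planned. With about 30 participants and 18 clips each, that is at most 30 × 18 = 540 frames, or 1,080 tracings in duplicate, plus a sentence or two of analysis text.
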